Determination of Sample Size	
The reference group proportion is 0.9800 according to the 3-year disease free survival rate reported in the previous literature on the subject of gastric GIST with maximum diameter between 2 to 5cm. -0.06 is set to detect a non-inferiority margin. The test statistic used is the one-sided Z test (unpooled). The significance level of the test is 0.025. The target Power is 0.80. The inconsistency rate between preoperative and postoperative pathological diagnosis of GIST from literature is about 30%. The dropout rate during follow-up is assumed to be 10%. The sample size needed by the study group was 182.

Number of Research Centers	13
Inclusion Criteria	
Diagnosed as gastrointestinal stromal tumor at unfavorable anatomic sites of stomach preoperatively by endoscopy, ultrasound endoscopy, CT or MRI;
 
Diameter of tumor size is ≥ 2cm and ≤ 5cm confirmed by contrast CT or MRI;
 
Patients whose tumor is resectable by laparoscopic techniques at preoperative assessment;
 
No evidence of distant metastasis and tumor invading nearby organs at preoperative assessment;
 
Performance status of 0 or 1 on ECOG (Eastern Cooperative Oncology Group) scale;
 
ASA (American Society of Anesthesiology) score I, II, or III;
 
Written informed consent.

Exclusion Criteria	
Women during pregnancy or breast-feeding;
 
Severe mental disorder;
 
History of previous upper abdominal surgery (except laparoscopic cholecystectomy);
 
History of other malignant disease within the past five years;
 
History of previous neoadjuvant imatinib therapy;
 
History of unstable angina or myocardial infarction within the past six months
 
History of cerebrovascular accident within the past six months;
 
History of continuous systematic administration of corticosteroids within the past month;
 
Requirement of simultaneous surgery for other disease;
 
Emergency surgery due to complication (bleeding, obstruction or perforation);
 
FEV1 < 50% of predicted value.
 
Patients with GIST locates at favorable anatomic sites detected by contrast CT, MRI or ultrasound endoscopy at preoperative assessment;
 
Patients with GIST diameter < 2cm or >5cm detected by contrast CT or MRI;
 
Presence of distant metastasis or tumor invading nearby organs at preoperative assessment

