Withdrawal Criteria	
Patients postoperatively confirmed as non-GIST case by pathology;
 
 ● GIST Patients diagnosed with GIST at unfavorable anatomic site preoperatively but confirmed at favorable anatomic site intraoperatively; ● Patients confirmed as spontaneous tumor rupture, metastasis or invading nearby organs intraoperately; ● Requirement of simultaneous surgery for other disease; 
Sudden severe complications during the perioperative period (intolerable

	
surgery or anesthesia), which renders it unsuitable or unfeasible to implement the study treatment protocol as scheduled;
 
Patients confirmed to require emergency surgery by attending physicians due to changes in the patient's condition after enrolled into this study;
 
Patients who voluntarily quit or discontinue treatment for personal reasons at any stage after enrolled in this study;
 
Treatment implemented is proven to violate study protocol.

Intervention	Laparoscopic resection for GIST at unfavorable anatomic site of stomach will be conducted
Endpoints	
Primary Endpoint:
 
3-year disease-free survival rate (DFS)
 
Second Endpoints:
 
Success rate of laparoscopic surgery
 
Rate of intraoperative complication
 
Rate of Postoperative complication
 
3-year overall survival rate (OS)
 
Postoperative recovery course

Statistical considerations	
Statistical software SAS (version 9.4) will be used for statistical analysis.
 
The efficacy will be tested for non-inferiority with historical comparison and the safety indicators adopts descriptive analysis. All statistical tests will be conducted by bilateral test. The test level with statistical significance is 0.05.
 
The interval estimation of parameters is 95% confidence interval. K-M survival analysis and Cox regression model will be used for analysis of survival time data. Central effect analysis: mixed-effect model for quantitative measures, CMH method for qualitative measures, and hierarchical logistic regression model for grade variables, survival time variables will be evaluated and adjusted using a Cox regression model. The central effect analysis and subgroup analysis will be carried out according to the specific situation. Interim analysis of this study will be carried out.

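### Does an interim analysis announced without purpose, timing or boundary undermine the one-sided 0.025 for 3-year DFS?

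*Combined protocol and SAP*

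**What the plan says.** All of this comes from the Abstract of the combined protocol and SAP.

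- **Statistical considerations**, last sentence: "Interim analysis of this study will be carried out". The number of looks, endpoint, purpose, timing, boundary and reviewing body are not given.
- **Statistical considerations**, on what is tested: "The efficacy will be tested for non-inferiority with historical comparison and the safety indicators adopts descriptive analysis".
- **Statistical considerations**, on level: "All statistical tests will be conducted by bilateral test. The test level with statistical significance is 0.05".
- **Determination of Sample Size**: "The test statistic used is the one-sided Z test (unpooled). The significance level of the test is 0.025". The reference rate is 0.98, the margin is -0.06, power is 0.80 and the total is 182. No allowance for an interim is mentioned.
- **Research Purpose** and **Endpoints**: the aim is the safety of the laparoscopic resection. The primary endpoint is the 3-year DFS rate. Secondary endpoints are surgical success, intraoperative complications, postoperative complications, 3-year overall survival and recovery course.

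**The concern.** Testing the same endpoint twice at the full level gives two chances of a false claim. The plan commits to an interim without any condition, whereas the sentence before it leaves centre-effect and subgroup analyses to circumstances. In the same row efficacy is tested and safety is only described, so a reader may suppose that whatever is tested at the interim is efficacy. The only level available would then be the full one, since none is set aside.

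The stake would be the primary claim. The null rate is 0.98 - 0.06 = 0.92, so decisions turn on a handful of events. Under an exact test, 45 event-free patients would already give p = 0.92^45 = 0.0235, below 0.025. The trial is also open-label with one arm, so outcomes are visible as they accrue.

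**Working it through.** **1. Inputs.** From the Abstract: reference 0.98, margin -0.06, one-sided 0.025, power 0.80, diagnosis mismatch 30%, dropout 10%, N = 182. Assumed, because the plan does not give them: the interim timing, and the evaluable number at the final analysis. The latter is either 182 × 0.7 × 0.9 = 114.7 (take 114) or, with losses added, 182 × 0.6 = 109.2 (take 109).

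**2. The plan's own figure.** An unpooled Z non-inferiority test with continuity correction first reaches power 0.80 at 115 evaluable. Then 115/0.7 = 164.3, rounded to 164, and 164/0.9 = 182.2, rounded to 182. As a back-check, an exact one-sample test of 0.92 against 0.98 has power 0.805 at 114. Neither route contains an interim adjustment.

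**3. Level.** Two-sided 0.05 is 0.05/2 = 0.025 in the non-inferiority direction. The two rows agree, and the final test has the full 0.025.

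**4. Interim without a DFS success test.** The only chance of a false claim is at the end. With the exact test at 114, at most 3 events are allowed, and P(X ≤ 3 | 114, 0.08) = 0.0162. A descriptive, safety or conduct interim leaves this unchanged. A futility-only look can only lower it.

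**5. Interim with an unadjusted DFS success test.** Let n1 patients be seen at the interim and n at the end, with c1 and c events allowed. The overall error is

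P(X1 ≤ c1) + Σ over i from c1+1 to c of P(X1 = i) × P(X2 ≤ c - i),

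where X1 has n1 patients, X2 has n - n1, and the event probability is 0.08.

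For 57 then 114, c1 = 0 and c = 3:

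- Interim: 0.92^57 = 0.0086.
- Final: 0.0428 × 0.1555 + 0.1041 × 0.0514 + 0.1660 × 0.0086 = 0.0134.
- Total: 0.0221 before rounding of the parts.

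| Interim / final | Overall error | Final look alone |
|---|---|---|
| 28 / 114 (25%) | 0.016 | 0.016 |
| 57 / 114 (50%) | 0.022 | 0.016 |
| 85 / 114 (75%) | 0.019 | 0.016 |
| 45 / 114 (worst timing) | 0.035 | 0.016 |
| 54 / 109 | 0.029 | 0.022 |
| 45 / 109 (worst timing) | 0.040 | 0.022 |

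For interims placed between 25% and 80% of the final number, 0.025 is exceeded at 19 of 64 timings (30%) with 114 evaluable, and at 31 of 61 (51%) with 109.

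**6. Normal approximation.** Two looks at z = 1.96 with correlation √t give 0.045, 0.042 and 0.037 at t = 0.25, 0.50 and 0.75. These overstate the exact result at 114. Only 114 × 0.08 = 9.1 events are expected under the null, and the exact test cannot reject before 45 patients (0.92^44 = 0.0255, 0.92^45 = 0.0235). The first of the three figures therefore describes an early claim that the exact test cannot make.

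**The case for a change.** The strongest opposing case is that silence is itself the fault. The interim is promised outright, no level is reserved, and a sentence naming its purpose would cost no patients and no power. The harm is also not confined to odd timings: with 109 evaluable, about half of the timings examined exceed 0.025. The test named in the sample-size row does worst. A one-sample unpooled Z allows 1 event in 57 and 4 in 114, for an overall error of 0.078.

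The arithmetic stands, and so does the observation that the interim is undescribed. Two things weaken the inference. First, every excess figure needs DFS to be tested early for success, and no sentence in the plan says so. The sentences on test level are general and do not mention the interim. Second, most of the 0.078 is not due to the interim: 0.045 is there with a single look, and the interim adds 0.078 - 0.045 = 0.033. The plan does not specify that one-sample form either. How the final test statistic behaves in small samples is a separate question.

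The lack of an interim allowance in 182 settles nothing either way. It fits an interim that leaves DFS alone, but an O'Brien-Fleming type boundary with two equal looks would raise N only by a factor of 1.008, to about 184.

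**Conclusion.** The concern does not hold as an error in the plan. The interim is undescribed, but carrying it out as a safety, conduct, descriptive or futility-only review complies with the text and leaves the one-sided 0.025 for 3-year DFS intact. That is also the natural reading. The stated aim is safety, and surgical success and complication rates are known long before 3-year DFS can be assessed. An analyst preparing a first non-inferiority test of DFS would see that the level is fully committed to the final look.

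The risk is conditional. If DFS were tested for success without adjustment, the overall error would be about 0.016 to 0.040 under an exact test of 0.92 with 109 to 114 evaluable. At 114 it would stay below 0.025 for looks at 25%, 50% and 75%. These figures rest on assumed timing, assumed evaluable numbers and a binomial analysis; the plan also names Kaplan-Meier methods for survival data. The text available is a synopsis, so a single closing sentence there is weak evidence that no fuller interim plan exists. This is missing detail with a sensible default, and no change to the plan is needed.
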